### 10.3.1 Efficacy Analyses

| Endpoint    | Statistical Analysis Methods  |
|-------------|---|
| Primary     | 
The primary analysis, on the change from baseline in NSAA total score, will be conducted using a Mixed Model Repeated Measures (MMRM) analysis with treatment, visit, and the treatment-by-visit interaction entered into the model as fixed effects, and participant entered as a random effect. The baseline NSAA total score will be entered into the model as a covariate. The stratification factors will be entered into the model as blocks.
 
For each RO7239361 dose group, the null hypothesis of the no treatment difference between the dose group and placebo will be tested using the estimates from this MMRM model at the end of the 48-week double-blind treatment period. In order to control the overall type I error rate for the analysis, the following hierarchical testing of doses will be implemented:
 
 
1. Comparison of the RO7239361 high dose (35/50 mg) to placebo at a two-sided <math>\alpha</math> level of 0.05 is performed.
 
2. If the null hypothesis for the high dose is rejected (comparison of the high dose to placebo in the previous step is statistically significant), then a comparison of the RO7239361 low dose (7.5/15 mg) to placebo at a two-sided <math>\alpha</math> level of 0.05 will be performed. If the null hypothesis for the high dose is not rejected, then the testing of the low dose versus placebo will not be performed.
 
 
Sensitivity analyses will include the following: an analysis of covariance (ANCOVA) using the mITT data set; an ANCOVA on the mITT data set with missing data imputed using multiple imputations; and an MMRM analysis using the per-protocol data.
 |

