2.2.2 Secondary Efficacy Endpoints

Secondary efficacy endpoints include:

- Change from baseline at Week 48 in:
 - Functional Testing:
 - 4-stair climb velocity (4SCV)
 - 4-stair climb time
 - Stand from supine velocity
 - 10-meter walk/run velocity
 - Proximal lower extremity flexor (knee extension and knee flexion) strength (kg), measured using manual myometry
 - 6 Minute Walk Distance (6MWD)
 - 95th percentile stride velocity recorded with ActiMyo (in a subset of the overall study population)
 - Observer Reported Outcome:
 - Parent-reported Pediatric Outcomes Data Collection Instrument (PODCI) transfers and basic mobility subscale
- No change/improvement in clinical impressions as measured by Clinical Global Impression of Change (CGI-C) at week 48.

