2.3 DETERMINATION OF SAMPLE SIZE

The sample size of 159 subjects (53 subjects per arm) will provide 80% power for testing the null hypothesis of no difference between a dose of RO7239361 and placebo, and 90% power for testing the null hypothesis of no difference between the pooled doses of RO7239361 and placebo, at a 2-sided α -level of 0.05 in the change from baseline in NSAA total score at 48 weeks, under the following assumptions:

- A true treatment difference (RO7239361 minus placebo) of 2.5 points
- A standard deviation of 4.4 points
- A treatment discontinuation rate of 5%.

For this study design and analysis, the minimum detectable difference is approximately 1.53 points for the comparison of the pooled dose groups to placebo, and 1.75 points for the comparison of an individual dose group to placebo.

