3.1 RANDOMIZATION

Subjects will be randomized to receive either low or high dose of RO7239361 or placebo according to a computer-generated randomization scheme.

During the screening visit, the investigative site will enter into the enrollment option of the Interactive Web Response System (IWRS) designated by Roche for assignment of a

subject number that will be unique across all sites. Once it is determined that the subject meets the eligibility criteria following the screening visit, the investigative site will enter into the IWRS to randomize the subject to one of the double-blind treatment groups.

Eligible subjects will be randomized in a 1:1:1 ratio to high dose RO7239361 (35/50 mg), low dose RO7239361 (7.5/15 mg), or placebo. The randomization will be stratified by:

- Age (6 through 7 vs 8 through 11)
- CS regimen: daily (prednisone, prednisolone or deflazacort) vs intermittent (any non-daily dosing of prednisone, prednisolone or deflazacort).

After 48 weeks on double-blind treatment, subjects continuing on study treatment will enter the open-label period. Placebo subjects will be re-randomized through IWRS and assigned to one of the RO7239361 dose groups.

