4.4 EFFICACY ANALYSIS AT END OF DOUBLE-BLIND TREATMENT

4.4.1 Primary Efficacy Endpoint

The primary analysis, on the change from baseline in NSAA total score after 48 weeks of double-blind treatment, will be conducted using a Mixed Model Repeated Measures (MMRM) analysis with treatment, visit, treatment-by-visit interaction, age stratum, and CS stratum entered into the model as fixed effects, and subject entered as a random effect. The baseline value of the NSAA total score will be entered into the model as a covariate. The modified ITT population will be the analysis population for the primary

efficacy analysis. An unstructured correlation within subject will be used. In the case that this does not converge, a compound symmetry structure will be used.

For each RO7239361 dose group, the null hypothesis of no treatment difference between the dose group and placebo will be tested using the estimates from this MMRM model at the end of the 48-week double-blind treatment period. In order to control the overall Type I error rate for the analysis of the primary endpoint, the following testing procedure (based on the closed testing principle) will be implemented:

1. Comparison of the pooled RO7239361 doses to placebo (intersection hypothesis) at a 2-sided α -level of 0.05 is performed.
2. If the result from the previous step is significant, then a comparison of the RO7239361 high dose (35/50 mg) to placebo and a comparison of the low dose (7.5/15 mg) to placebo will both be performed at a 2-sided α -level of 0.05.

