4.4.2 Secondary Efficacy Endpoints

The secondary efficacy analyses will compare the change from baseline to week 48 between each RO7239361 dose group and the placebo group, for the following endpoints.

- 4SCV
- 6MWD
- 95% stride velocity (SV95C)
- Stand from supine velocity
- 10-meter walk/run velocity
- PODCI transfers and basic mobility subscale
- Proximal lower extremity flexor (knee extension and knee flexion) strength measured using manual myometry
- CGI-C

MMRM models similar in structure to that used for the primary analysis will be used for the continuous secondary efficacy endpoints, with the exception of proximal lower extremity flexor strength (which will be tested using a multivariate analysis of variance of the 2 component variables: knee extension and knee flexion).

The distribution of CGI-C and CaCGI-C responses at week 48 will be summarized using descriptive statistics. Categorical analysis of the number of subjects falling into pre-specified categories (i.e., 'any improvement or no change' vs. 'any worsening') will be performed using a Cochran-Mantel-Haenszel test using age category and CS use as stratification factors.

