4.4.4 Sensitivity Analyses

In order to assess the impact of the presence of missing data on the results of the primary and secondary efficacy analyses using an MMRM analysis, additional analyses may be performed using methodologies such as multiple imputation methods with pattern mixture models. Final specifications of the methods used to handle missing data in these additional analyses will be finalized prior to the primary efficacy analysis, and will be determined based on characteristics including the proportion of subjects discontinuing treatment, and the reasons for discontinuation. The rate of missing data is expected, however, to be low.

For selected continuous efficacy endpoints, additional analyses may be performed using:

- an analysis of covariance (ANCOVA) model on the mITT data set using the observed change from baseline at week 48 as the dependent variable, treatment, age stratum, and CS stratum as fixed effects, and baseline value as a covariate.
- ANCOVA (at week 48) and MMRM models on the mITT data set with missing data imputed using multiple imputations with pattern mixture models
- an MMRM analysis using the per-protocol analysis population.

In this population, the treatment discontinuation and study discontinuation rates during the 48-week double-blind treatment period are expected to be low (as reflected in the 5% assumed treatment discontinuation rate incorporated into the sample size calculation).

This expectation is based on:

- the low treatment discontinuation rate, and overall safety and tolerability profile of RO7239361, to date from the ongoing WN40226 study
- the treatment discontinuation rates in the phase III 48-week double-blind studies in with ataluren and drisapersen DMD ambulatory patients
- the relatively short (compared to other competing clinical trials in DMD patients) double-blind treatment duration of 48 weeks
- the inclusion of a safety follow up visit (which also includes an NSAA assessment) for those subjects who discontinue, which should reduce the number of missing assessments of the primary efficacy endpoint.

It is not expected that there will be other frequently occurring intercurrent events (i.e., introduction of rescue medications) that will materially affect the efficacy assessments or that could motivate a decision to exclude values recorded after such an event.

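### SAP 4.4.1 gives the primary MMRM one fallback, compound symmetry of unstated form; the ordinary form mis-sizes the Week 48 standard error whenever Week 48 variance differs from the visit average

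*SAP*

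**What the plan says.** SAP 4.4.1 models change from baseline in NSAA total score. The fixed effects are treatment, visit, their interaction, age stratum and corticosteroid stratum. Baseline NSAA is a covariate and subject is a random effect. The within-subject correlation is unstructured, and then: "In the case that this does not converge, a compound symmetry structure will be used". No other structure, robust variance or degrees-of-freedom method is named. Protocol 10.3.1 names no covariance structure.

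The schedule in Protocol Table 2-2 gives four post-baseline NSAA visits (Weeks 12, 24, 36 and 48). Only the estimate at the end of the 48 weeks is tested.

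SAP 2.3 assumes "A standard deviation of 4.4 points" and gives no SD by visit. It states a minimum detectable difference of "1.75 points for the comparison of an individual dose group to placebo".

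SAP 4.4.2 adds that "MMRM models similar in structure to that used for the primary analysis will be used for the continuous secondary efficacy endpoints". It does not say whether the fallback carries over.

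**The concern.** An unstructured matrix lets Week 48 have its own variance. Ordinary compound symmetry does not: it fits one variance for all visits and applies it to the Week 48 contrast. If the fallback is used, that single sentence determines the standard error of the primary test, and through it the closed test of the doses and the secondary hierarchy.

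The form is also unstated. One programmer could fit homogeneous compound symmetry and another the heterogeneous form, and they would get different primary p-values from the same data.

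The random subject effect makes this worse. A 4x4 unstructured matrix already has 4 × 5 / 2 = 10 free parameters. A random intercept adds an eleventh, but it only adds a constant to every element of a matrix that is already free. Ten quantities are identified for eleven parameters. Fitted literally, this could produce the failure that triggers the fallback.

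**Working it through.** **Inputs from the documents.** SD 4.4, difference 2.5, two-sided alpha 0.05 (SAP 2.3); about 150 evaluable boys, so 50 per arm (Protocol synopsis); four visits (Table 2-2). The SDs at Weeks 12, 24 and 36 below are assumptions, and every path ends at 4.4.

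**The plan's own figure.** The Week 48 SE is 4.4 × √(2/50) = 0.880. The smallest significant difference is t(0.975, 98 df) × 0.880 = 1.746, which matches the SAP's 1.75. Power for 2.5 points is Φ(2.5/0.880 − 1.96) = 81%, against the stated 80%.

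**Effect of homogeneous compound symmetry.** With complete data and free treatment-by-visit means, the fitted common variance is the mean of the four visit variances. So:

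- ratio r = √(mean variance / 4.4²) = √(mean variance / 19.36)
- actual two-sided error = 2 × [1 − Φ(1.96 r)]
- difference needed for significance = 1.75 r

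Example, SDs 2.2/3.1/3.8/4.4: mean variance = (4.84 + 9.61 + 14.44 + 19.36)/4 = 12.06; r = √(12.06/19.36) = 0.789; error = 12.2%; difference needed = 1.38.

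| Assumed SD, Weeks 12/24/36/48 | Mean variance | r | Difference needed | Error (formula) | Error (simulated), homogeneous CS | Error (simulated), three heterogeneous structures |
|---|---|---|---|---|---|---|
| 5.2/4.9/4.6/4.4 | 22.89 | 1.087 | 1.90 | 3.3% | 3.2% | 4.1–4.6% |
| 4.4 throughout | 19.36 | 1.000 | 1.75 | 5.0% | 5.0% | 4.3–5.0% |
| 3.5/3.8/4.1/4.4 | 15.71 | 0.901 | 1.58 | 7.7% | 6.9% | 3.7–4.5% |
| 2.95/3.3/3.8/4.4 | 13.35 | 0.830 | 1.45 | 10.4% | 10.9% | 4.5–5.2% |
| 2.2/3.1/3.8/4.4 | 12.06 | 0.789 | 1.38 | 12.2% | 12.0% | 4.4–4.9% |

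In the falling case, power for 2.5 points is Φ(2.841 − 1.96 × 1.087) = 76% instead of 81%.

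Constant spread is sufficient but not necessary. With SDs 4.0/4.4/4.77/4.4 the mean variance is 19.37, r is 1.000, and the SE is right.

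**Simulation.** 2,000 null trials per path, 53 per arm, 5% monotone dropout, true correlation 0.8^lag, the SAP's fixed effects, REML, model-based SEs, t with 147 df. Monte Carlo SE is about 0.5 percentage points at 5% and 0.7 at 12%. The simulated errors are for high dose against placebo. Familywise error of the SAP's closed test, in the table's row order, was 2.6/4.1/6.7/9.6/10.7% with homogeneous compound symmetry and 3.4–4.5% with the heterogeneous structures. The true correlation favours AR(1) and Toeplitz. Heterogeneous compound symmetry is misspecified here and still held (3.7–4.5%).

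**Overall error.** If the fallback is reached with probability p, unrelated to the treatment result, overall error = 0.05 + p × (conditional error − 0.05). For the three rising paths:

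- p = 1%: 0.05 + 0.01 × (0.077 to 0.122 − 0.05) = 5.0–5.1%
- p = 5%: 0.05 + 0.05 × (0.077 to 0.122 − 0.05) = 5.1–5.4%

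For the falling path at p = 5% it is 0.05 − 0.05 × 0.017 = 4.9%.

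**The case against.** **The fallback will rarely be used.** With four visits and about 150 boys, an unstructured fit normally converges. In 600 simulated trials (constant, rising and falling SDs, 200 each, no separate random subject effect) every fit converged. This stands, and it is why the overall effect is small. It does not cover the model as literally written, with the added random effect.

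**The wording may allow the heterogeneous form.** The preceding SAP sentence speaks of correlation, so a compound-symmetric correlation with visit-specific variances is a possible reading and would remove the problem. This also stands; it is a reason to state the form.

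**A Week 48 ANCOVA sits alongside.** Protocol 10.3.1 says: "Sensitivity analyses will include the following: an analysis of covariance (ANCOVA) using the mITT data set". SAP 4.4.4 softens this: "For selected continuous efficacy endpoints, additional analyses may be performed using". An ANCOVA on Week 48 data uses only that visit's variance and would expose a discrepancy, but it does not replace the primary test.

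**A stronger reading to avoid.** A reader might infer from Protocol 3.1.3 (a gain of 4 linearized units a year up to age 7, then a loss of 8 a year) that spread must rise and the test must be anti-conservative. The documents do not support that. The age groups diverge by 12 units a year, or 2.8/5.5/8.3/11.1 units at the four visits. Once the model's age main effect removes the average gap of 6.9, −4.2/−1.4/+1.4/+4.2 remains, which is as large at Week 12 as at Week 48. Randomization is also stratified by age. Simulating these courses with constant SD 4.4, an assumed 60% aged 8 to 11, and 0.375 or 0.5 raw points per linearized unit gave 4.5% and 4.9% error under homogeneous compound symmetry (4,000 trials each).

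**Conclusion.** The point holds as a cheap improvement to the SAP. Under the homogeneous reading, the fallback gives the Week 48 test the wrong SE whenever Week 48 variance differs from the average of the four visits. The documents fix neither the direction nor the size, and all non-constant SD paths here are assumptions.

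The 3.3% to 12.2% range is conditional on the fallback being used. A reader might take 12.2% as the trial's error rate; it is not. The algebra is secure. How often the fit would fail is not known, and the random-effect clause is a reason it might fail more often than the visit count suggests.

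**What to change.** Before unblinding, make three changes to the SAP.

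1. In 4.4.1, state that the unstructured matrix models the within-subject covariance and that no separate random subject effect is fitted.
2. Replace the fallback sentence with: *If the unstructured covariance does not converge, the following will be tried in order until one converges: heterogeneous Toeplitz, heterogeneous AR(1), heterogeneous compound symmetry.*
3. In 4.4.2, state whether the same rule applies to the continuous secondary MMRMs. Myometry (MANOVA) and CGI-C (Cochran-Mantel-Haenszel) are not affected.

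The cost is a few SAP sentences and slightly more programming. The structure and fallback list need no protocol amendment, because the protocol names no covariance structure. Protocol 10.3.1 does enter participant as a random effect, so the SAP should say that the unstructured matrix takes that role.

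If spread grows over time, the reported 95% half-width is about 1.75 points rather than the 1.38 to 1.58 that homogeneous compound symmetry would show. Heterogeneous compound symmetry was slightly conservative in simulation (mean SE 0.89 against an empirical 0.85 to 0.87). Convergence of the listed structures in trials where the unstructured fit had failed was not tested.

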4.4.2 Secondary Efficacy Endpoints

The secondary efficacy analyses will compare the change from baseline to week 48 between each RO7239361 dose group and the placebo group, for the following endpoints.

- 4SCV
- 6MWD
- 95% stride velocity (SV95C)
- Stand from supine velocity
- 10-meter walk/run velocity
- PODCI transfers and basic mobility subscale
- Proximal lower extremity flexor (knee extension and knee flexion) strength measured using manual myometry
- CGI-C

MMRM models similar in structure to that used for the primary analysis will be used for the continuous secondary efficacy endpoints, with the exception of proximal lower extremity flexor strength (which will be tested using a multivariate analysis of variance of the 2 component variables: knee extension and knee flexion).

The distribution of CGI-C and CaCGI-C responses at week 48 will be summarized using descriptive statistics. Categorical analysis of the number of subjects falling into pre-specified categories (i.e., 'any improvement or no change' vs. 'any worsening') will be performed using a Cochran-Mantel-Haenszel test using age category and CS use as stratification factors.

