| Upper & Lower Extremity Myometry | X                   |                        |                         |                         |                      |                  |                       | X                |                       |                  |                       | X                                | See Clinical Evaluator Manual; myometry assessment must be videotaped for ATOM review at D1, Wk 24 and Wk 48 visits   |
| Grip & Pinch Strength            | X                   |                        |                         |                         |                      |                  |                       | X                |                       |                  |                       | X                                | See Clinical Evaluator Manual   |
| PUL                              | X                   |                        |                         |                         |                      |                  |                       | X                |                       |                  |                       | X                                | See Clinical Evaluator Manual; PUL assessment must be videotaped for ATOM review at D1, Wk 24 and Wk 48 visits  |
| Right Ankle Range of Motion      | X                   |                        |                         |                         |                      |                  |                       | X                |                       |                  |                       | X                                | See Clinical Evaluator Manual   |
| Caregiver video assessment       | X                   |                        |                         |                         |                      | X                |                       | X                |                       | X                |                       | X                                | Subjects at selected sites who opt in will record videos at selected timepoints of the study (as specified), or at any applicable visits after start date. The visit window is +2 weeks. See Section 9.1.6 and the parent/caregiver manual. |

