| Secondary   | 
Following testing of the primary endpoint, the key secondary endpoints will be analyzed using a hierarchical testing procedure in order to maintain the overall type I error rate at 0.05. This procedure will be specified in the Statistical Analysis Plan prior to database lock.
 
Most secondary endpoints will be tested using a MMRM that is similar in structure to the primary analysis. Proximal lower extremity flexor strength will be tested using a MANOVA of the 2 component variables: knee extension and knee flexion.
 
If a dose fails to reach significance against placebo in any stage of the testing hierarchy, any further tests will be considered as exploratory.
   |
| Exploratory | Will be described in the Statistical Analysis Plan finalized before database lock   |

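### The knee-strength MANOVA on change from baseline names no baseline covariate, no randomisation stratum and no signed dose-minus-placebo estimate (minor)

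*SAP*

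**What the plan says.** SAP 4.4.2 opens by saying that the secondary analyses compare change from baseline to Week 48 between each dose group and placebo, and knee strength is in its list. Continuous secondaries get MMRM models similar to the primary. Knee strength is the one stated exception, tested by a "multivariate analysis of variance of the 2 component variables: knee extension and knee flexion". Protocol 10.3.1 agrees: "Proximal lower extremity flexor strength will be tested using a MANOVA of the 2 component variables: knee extension and knee flexion".

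Neither sentence names a covariate, a stratum, a test statistic or an estimate with a confidence interval. Three other places in the SAP matter:

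- **SAP 4.4.1:** the primary MMRM, from which knee strength is excepted, names the baseline value as a covariate and the age and CS strata as fixed effects.
- **SAP 4.4.2, CGI-C:** the Cochran-Mantel-Haenszel test names both stratification factors.
- **SAP 4.4.4:** an ANCOVA with baseline and both strata is allowed, but only as something that may be done for selected endpoints. Knee strength is not named there.

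The data exist. The row "Upper & Lower Extremity Myometry" in Protocol Table 2-2 is marked at Day 1, Week 24 and Week 48 (or early discontinuation). Knee strength is not among the six endpoints in the hierarchy of SAP 4.4.2.1.

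**The concern.** The protocol expects the drug to act mainly by enlarging existing muscle fibres (Protocol 3.1.2 and 3.2), so strength is the secondary endpoint closest to the mechanism. As written, its analysis has two weaknesses.

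1. **No direction.** A two-component MANOVA tests whether the pair of mean changes differs between groups. It does not say which group did better, and it can be significant when extension and flexion move in opposite directions. Without a signed difference and interval for each component, a significant p-value cannot be read as benefit.
2. **Unused information.** The component baselines and the randomisation strata are collected, and the models for the other continuous secondaries use them. Because the exception takes knee strength out of that model structure, nothing in the text carries those terms over. A Week 48 MANOVA would also ordinarily leave out a boy who has a Week 24 value but no Week 48 value, or who lacks one component. An MMRM keeps his observed data.

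**Working it through.** **Inputs from the plan.** SAP 2.3 gives "The sample size of 159 subjects (53 subjects per arm) will provide 80% power", tested "at a 2-sided α -level of 0.05 in the change from baseline in NSAA total score", with "A true treatment difference (RO7239361 minus placebo) of 2.5 points", "A standard deviation of 4.4 points" and 5% treatment discontinuation. That leaves 53 × 0.95 = 50.35, about 50 evaluable per arm.

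**The plan's own figure.** Standardised effect 2.5/4.4 = 0.568; noncentrality 0.568 × √(50/2) = 2.84. Power is 81.1% (normal) or 80.3% (t), against 80% stated. The plan's sample size reproduces, so 50 per arm is used below. The plan states no power for knee strength.

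**Assumed inputs.** The documents give no SD, effect, baseline-to-Week-48 correlation (rho) or between-component correlation (r) for knee strength. Ranges are shown instead. Effects are in SDs of the change score.

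**Direction.** For one dose against placebo with n per arm, the MANOVA is Hotelling's T², with noncentrality

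λ = (n/2) × (d1² + d2² - 2·r·d1·d2)/(1 - r²),

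referred to F with 2 and 2n - 3 = 97 degrees of freedom at n = 50.

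| Effects (extension, flexion) | λ, r = 0.6 | Power | λ, r = 0.3 | Power |
|---|---|---|---|---|
| +0.4, +0.4 | 5.0 | 49% | 6.15 | 58% |
| -0.4, -0.4 | 5.0 | 49% | 6.15 | 58% |
| +0.4, -0.4 | 20.0 | 98% | 11.43 | 86% |

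Worked for r = 0.6: same direction, 25 × 0.128/0.64 = 5.0; opposite directions, 25 × 0.512/0.64 = 20.0. Benefit and harm are equally likely to be declared, and opposite movements are the easiest to declare.

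**Precision from the baseline covariate.** With equal variances s² at baseline and Week 48:

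- variance of the change score: 2s²(1 - rho)
- residual variance with baseline as covariate: s²(1 - rho²)
- ratio (1 + rho)/2, so the cut is (1 - rho)/2

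| rho | Variance cut | λ for (+0.4, +0.4), r = 0.6 | Power |
|---|---|---|---|
| no covariate | none | 5.00 | 49% |
| 0.9 | 5% | 5.26 | 51% |
| 0.8 | 10% | 5.56 | 54% |
| 0.5 | 25% | 6.67 | 62% |

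The adjusted rows use 2 and 93 degrees of freedom, allowing four for two baselines and two strata. The cut is 15% at rho 0.7 and 2.5% at rho 0.95. Simulating MANOVA against MANCOVA with both baselines gave 49% v 50% (rho 0.9), 50% v 54% (0.8) and 48% v 61% (0.5).

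If the strata explained a further 5 to 10% of variance (assumed), the total cut would be about 10 to 15% at rho 0.9 and 29 to 33% at rho 0.5.

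**Two-df test against an averaged one-df test.** With n = 50 and r = 0.5, the average has λ = (n/2) × ((d1 + d2)/2)²/((1 + r)/2), referred to F with 1 and 98 degrees of freedom.

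| Effects | MANOVA | Average |
|---|---|---|
| 0.5, 0.5 | 72% | 82% |
| 0.5, 0.25 | 59% | 57% |
| 0.5, 0.1 | 64% | 40% |
| 0.5, 0 | 72% | 30% |

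The ranking depends on whether both muscle groups respond alike, and the documents give no expectation on that.

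**The case against.** Much can be said for the plan, and most of it stands.

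- **Baseline is not ignored.** A reader might infer that the test uses no baseline value. The response is change from baseline, so baseline enters by subtraction. Only baseline as a covariate is unnamed.
- **Silence is not exclusion.** A reader might infer that the sponsor chose an unadjusted test. Each document gives the test one clause, and neither says unadjusted. SAP 4.4.4 would permit an adjusted ANCOVA. But that analysis is optional and limited to selected endpoints, so it does not settle how knee strength will be tested.
- **A comparison by dose is planned.** A reader might infer that only a three-arm omnibus test is intended. SAP 4.4.2 commits to each dose against placebo. What it lacks is a signed estimate for this endpoint.
- **The two-df test is not simply inefficient.** A reader might infer that averaging the components would be more powerful. That holds only when both respond similarly. Keeping one test for a two-component endpoint is a defensible choice.
- **The precision gain may be small.** At rho 0.9, power moves from 49% to 51% in the example. Nothing in the documents points to a rho near 0.5.
- **Missing data are expected to be few.** SAP 4.4.4 says so, and no rate is given for boys lacking just one component. The loss of incomplete cases is therefore unquantified and probably minor.

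What remains uncontested is that no covariate, stratum or signed difference is specified, and that the MANOVA p-value alone cannot show benefit.

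**Conclusion.** The point holds as a minor one. The lack of direction is a property of the test, whatever the assumptions; the 49%, 49% and 98% rest on the assumed 0.4 SD effects and r = 0.6. The precision loss is certain only in kind. Its size, 5% of residual variance at rho 0.9 to 25% at rho 0.5, assumes equal variances and a correlation that the documents do not give.

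A reader might infer a threat to the trial's main conclusions. The documents do not support that: knee strength is outside the six-endpoint hierarchy, so the primary result and type I error are unaffected. What is at stake is whether the strength result can be interpreted and uses the information collected.

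**What to change.** In SAP 4.4.2, with a matching clarification in Protocol 10.3.1:

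1. Make the test a MANCOVA of change at Week 48 in knee extension and knee flexion, with both component baselines and the age and CS strata, for each dose against placebo.
2. Report each component's dose-minus-placebo difference at Week 48, with its confidence interval, from the MMRM used for the other continuous secondaries: change at Weeks 24 and 48, treatment, visit, treatment-by-visit, component baseline and both strata.
3. State that a significant multivariate test is read as benefit only alongside these signed differences.

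An averaged one-df test is not proposed. The cost is a few lines of SAP text and the protocol clarification: no new visits, measurements or participants, and no effect on alpha.
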